7.9.3 Secondary Performance Variables

All secondary clinical performance endpoints will be presented with descriptive statistics. The following binary secondary clinical performance endpoints will show the endpoint estimate together with a two-sided 95% CI based on the Wilson score.

- Proportion of patients having a continued clinical response to treatment at Day 25, defined as the proportion of patients clinically cured on Day 7-14 (taking into account the intercurrent events and applying the composite strategy as described in Section 7.9.1) and thereafter responding "no" to the yes/no question, "Have the symptoms recurred?" and no rescue medication has been given up to day 25
- Proportion of patients having a cure defined as clinical cure Day 7-14 according to primary endpoint (taking into account the intercurrent events and applying the composite strategy as described in Section 7.9.1) and mycological cure at Day 7-14 (culture negative for growth of Candida species).
- Proportion of patients having a reduction in CVVS score on Day 7-14 compared to Day 0.
- Proportion of patients having a reduction in the sum of the 3 vulvovaginal symptoms scores (itching, burning, and irritation) on Days 1 to 7, Day 11, Day 14 and Day 25, compared to Day 0.
- Proportion of patients having a mycological cure as assessed by vaginal culture on Day 7-14 and Day 25.
- Proportion of patients having an absence of Candida hyphae in the wet smear on Day 7-14.

Statistical Analysis Plan

Study ID: CL4

Presentation of the continuous secondary clinical performance endpoints below will include the two-sided 95% CIs for the arithmetic mean.

- The change in CVVS score from Day 0 to Day 7-14 (last available assessment).
- Change in the sum of the 3 vulvovaginal symptoms scores (itching, burning, and irritation) to each post baseline assessment.

Usability will be measured on Day 6, by a patient questionnaire (see Appendix 1). The questionnaire contains 2 yes/no (i.e. binary) variables, 2 categorical variables and the question, "How do you generally regard the treatment?", rated on a 1-10 integer scale. These endpoints will be presented descriptively, treating the question rated on the 1-10 scale as a continuous variable. In case of multiple assessments of usability, the first non-missing value will be used.

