The diagnosis of VVC in the study is based on the FDA Guidance for Industry. The FDA recommendation is that the patients should have 1) 2 or more of the following signs and symptoms: itching, burning, irritation, edema, erythema, or excoriation; 2) Potassium hydroxide (KOH) or saline preparation from the inflamed vaginal mucosa or secretions demonstrating yeast forms (hyphae or pseudohyphae) or budding yeasts, and 3) vaginal pH ≤ 4.5 . However, in this study, pH ≤ 4.5 will not be an inclusion criterion. The low risk profile of the Gedea Pessary allows this less stringent inclusion criteria and the VVC diagnosis will be confirmed post inclusion, by both vaginal culture and microbiome analysis.

The VVC diagnosis will be validated by culture and microbiome analysis. The vaginal microbiome will be analysed to better understand the relation between vaginal dysbiosis and VVC.

To fulfil the primary endpoint (clinical cure), signs and symptoms of VVC must be absent and this is defined in terms of having a CVVS score ≤ 3 . This is consistent with the current FDA guidelines and the CVVS score is an established method to define VVC signs and symptoms and clinical cure. ⁵³

The safety endpoints were selected to assure a sufficient method to assess the safety of the Gedea Pessary. The usability endpoint was selected to ensure the Gedea Pessary is easy to use for the patients.

The dose of 150 mg GDL and 184 mg NaG administered daily for 6 days was chosen based on clinical data from previous studies (see [Section 3.3.2](#)). Also, pre-clinical measurements of pH in an *in vitro* dissolution test have shown a pH decrease duration of approximately 24 hours for the *p*Hyph gen II (see the IB).

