5.4.1 Day 0; Screening and enrolment

Patients seeking treatment for symptoms relating to VVC may be informed about the study and, if agree to participate, sign the ICF. After the ICF is signed, patients will undergo a gynaecological examinations, where the Investigator or an authorised designee will assess the presence of vulvovaginal signs (erythema, oedema, or excoriation) and symptoms (itching, burning, or irritation) and score each sign and symptom, as described in [Section 9.1](#).

Vaginal samples will be examined under a microscope for yeast forms (hyphae or pseudohyphae) or budding yeast. Two vaginal secretion samples will also be collected by a vaginal swab. One sample will be cultured to verify the presence of *Candida* and the other (taken in duplicates) will be used for sequencing analysis of the vaginal microbiome prior to treatment ([Section 10.1.1](#)). If the Investigator assesses that the patient has VVC, based on the gynaecological examination and the fungal microscopy, the patient will receive the investigational product to be self-inserted vaginally at home during 6 consecutive days (Days 0 to 5). In addition, the Investigator will measure the vaginal pH, as described in [Section 10.1.2](#).

The Investigator or delegatee will ask the patient about onset and end of last menstruation. The patient should not be enrolled, or the enrolment should be postponed, if menstruation is foreseen to occur at the time of the Day 7 visit.

Procedures to be performed:

- Informed consent
- Demography
- Eligibility criteria
- Pregnancy test (urinary)
- Recording of
 - Medical and surgical history
 - Prior and concomitant medications
 - Onset and end of last menstruation
- Gynaecological examination by Investigator or authorised designee, evaluating vulvovaginal signs (erythema, oedema, and excoriation) and symptoms (itching, burning, and irritation) according to a scoring scale (0-3).
- Fungal microscopy assessment (KOH or saline preparation)
- Vaginal swab for:
 - Culture
 - Sequencing
- Vaginal pH
- Treatment dispensing for self-administration by patients at home.

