5.4.3 Day 7 (+2 days); Follow-up visit

Patients will visit the clinic on Day 7 to have gynaecological examination performed. The Investigator or an authorised designee will assess the presence of vulvovaginal signs (erythema, oedema, and excoriation) and symptoms (itching, burning, and irritation) and score each sign and symptom on a scale of 0 to 3 (see [Section 9.1.2](#)).

Vaginal samples will be examined under a microscope for yeast forms (hyphae or pseudohyphae) or budding yeast. Vaginal secretion samples collected by swabs will be used for culture and for sequencing analysis of the vaginal microbiome (this sample will be taken in duplicates). If the patient is menstruating at this timepoint, the visit should be postponed until the menstruation is over, even though the visit will happen outside the visit window.

Procedures to be performed:

- Gynaecological examination by Investigator or authorised designee, evaluating vulvovaginal signs (erythema, oedema, and excoriation) and symptoms (itching, burning, and irritation) according to the scoring scale (0 to 3).
- Fungal saline microscopy assessment
- Vaginal swab for
 - Culture
 - Sequencing
- Vaginal self-swab for:
 - Sequencing
- Vaginal pH
- Recording of
 - Concomitant medications
 - AEs
 - Potential menstruation onset
- Product accountability – patients should be asked to return all used and not used treatment packages

Rescue treatment, according to standard clinical practice, will be offered if the intensity of the VVC symptoms is the same or higher compared to the inclusion visit (Visit 1, Day 0). See details in [Section 7.5.2](#).

An assessment of mycological cure will be done as soon as the results from the laboratory are received. A mycological cure is defined as no presence of *Candida* species. If the patient has both a clinical and mycological cure at Day 7, the Day 14 visit should be cancelled.

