6.3 Inclusion criteria

1. Having decisional capacity and providing written informed consent.
2. Adult, post-menarchal, pre-menopausal women, aged 18 years or older
3. Diagnosis of VVC, defined as:
 - o Having a white or creamy vaginal discharge

- At least 2 of the following signs and symptoms of VVC that are characterised as at least moderate^a: itching, burning, irritation, oedema, erythema, or excoriation.
- KOH or saline preparation from the inflamed vaginal mucosa or secretions revealing yeast forms (hyphae or pseudohyphae) or budding yeasts.

4. Negative urine pregnancy test at Screening.
5. Refrain from using any intravaginal products (i.e. contraceptive creams, gels, foams, sponges, lubricants, or tampons, etc.) until Day 14.
6. Refrain from sexual intercourse or use a condom until Day 7.
7. Signed informed consent and willing and able to comply with all study requirements.

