6.6 Microbiology assessment

Vaginal samples will be collected via a vaginal swab by the Investigator or delegatee on site visits (Day 0, Day 7 and Day 14) or by patients themselves at home, on Day 25.

The collected samples will be used for the following analyses.

- **Microscopic analysis; presence of hyphae:** KOH or saline test for fungus, using samples collected on Day 0, Day 7 and Day 14. Briefly, vaginal samples will be covered with 10% to 20% KOH, or 0.9% isotonic NaCl solution, and inspected under a microscope. Presence of hyphae

Study ID: CL4

- indicates Candida and will serve as an immediate, preliminary VVC diagnosis (present, absent, traced).
- **Candida culture:** Samples collected on Days 0, 7, 14 and 25, will be sent to laboratory for culture and confirmation of the VVC diagnosis/mycological cure. Vaginal swab culture result (positive, negative) and species present (C.albicans, C. tropicalis, C. glabrata, C. krusei, Other) will be recorded in the eCRF.
- **Sequencing of the vaginal microbiome:** Vaginal swabs for sequencing of the vaginal microbiome will be collected on Days 0, 7, 14, and 25. The effects of the investigational product on the vaginal microbiome will be assessed. Collected samples will be sent to a central laboratory for assessment of bacterial and fungus species, through DNA sequencing.

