7.2.1 Full Analysis Set

The full analysis set (FAS) is defined as all subjects who received at least one administration of the investigational product.

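### Endpoints 3, 8 and 9 are scored on the follow-up result alone, so they do not measure conversion in women who were culture-negative or free of hyphae at Day 0; a supportive row would fix this

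*SAP*

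**What the plan says.** SAP 7.9.3 defines endpoint 8 as the "Proportion of patients having a mycological cure as assessed by vaginal culture on Day 7-14 and Day 25" and endpoint 9 as the "Proportion of patients having an absence of Candida hyphae in the wet smear on Day 7-14". Endpoint 3 combines clinical cure on Day 7-14 with a culture showing no *Candida* growth. Protocol 5.4.3 supplies the underlying definition: "A mycological cure is defined as no presence of" *Candida* species. None of these mentions Day 0, whereas the CVVS and symptom-score endpoints in the same list are stated relative to Day 0.

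On entry, Protocol 6.3 asks for discharge, at least two signs or symptoms of at least moderate grade, and a "KOH or saline preparation from the inflamed vaginal mucosa or secretions revealing yeast forms (hyphae or pseudohyphae) or budding yeasts". Budding yeasts alone are enough. Protocol 5.4.1 says that, if VVC is diagnosed "based on the gynaecological examination and the fungal microscopy, the patient will receive the investigational product". Culture comes later: under Protocol 5.2, "the VVC diagnosis will be confirmed post inclusion, by both vaginal culture and microbiome analysis", with no consequence stated for a negative culture.

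The FAS (SAP 7.2.1) is "defined as all subjects who received at least one administration of the investigational product", and SAP 7.9 makes it the main analysis set. Exclusions from the PPAS and PPAS25 are left to the clean file meeting (SAP 7.2.2, 7.2.3).

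**The concern.** A woman can be treated and analysed while culture-negative at Day 0, or with budding yeasts but no hyphae. If she is still negative on that test at follow-up, she counts as a success for endpoint 8 or 9, and for endpoint 3 if she is also clinically cured. The rates then mix two groups: women whose test changed, and women whose test was negative throughout.

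The study has one arm, so the woman's own baseline is the only reference for change. A reader who sees the word cure on endpoints 3 and 8 may well take it to mean conversion.

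Two limits apply. Culture-negative entrants were still microscopy-positive, so the point is that conversion is not measured, not that these women had no fungus. For endpoint 3 only the mycological half is affected: two items scored at least 2 give a Day 0 CVVS of at least 4, above the cure cut-off of 3, so the clinical half does require a change.

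**Working it through.** **The plan's own figure.** The documents give no planning figure for endpoints 3, 8 or 9. The only one is the primary sample size (Protocol 12.6, SAP 5.1): 30% against 54%, one-sided 5%, 80% power. The normal approximation gives

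n = [(1.645·√(0.30·0.70) + 0.842·√(0.54·0.46)) / 0.24]² = 23.90, rounded up to 24.

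This matches. The concern changes neither this figure nor N = 26.

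**Inputs.** N = 26 with none missing, and two-sided 95% Wilson intervals (SAP 7.9.3). Three quantities are not in the documents and are assumed:
- k: women negative at Day 0 on the test in question (it may differ between culture and hyphae)
- p: clearance among Day 0 positives
- q: chance that a Day 0 negative is also negative at follow-up

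**Endpoints 8 and 9.** FAS rate = [kq + (26 − k)p]/26, so the shift against p is (k/26)(q − p). In percentage points:

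| k | q=100%, p=70% | q=100%, p=30% | q=70%, p=30% | q=50%, p=70% |
|---|---|---|---|---|
| 0 | 0 | 0 | 0 | 0 |
| 1 | +1.2 | +2.7 | +1.5 | −0.8 |
| 3 | +3.5 | +8.1 | +4.6 | −2.3 |
| 5 | +5.8 | +13.5 | +7.7 | −3.8 |

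**Endpoint 3.** Take 54% clinical cure, assumed independent of culture. The shift is (k/26)·0.54·(q − p). For k = 3, in the same column order: +1.9, +4.4, +2.5 and −1.2 points.

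**Worked example, k = 3.** Suppose 9 of 23 positives clear: 39.1% (22.2 to 59.2). The FAS rate depends on the three negatives:
- all 3 negative at follow-up: 12/26 = 46.2% (28.8 to 64.5)
- 2 negative: 11/26 = 42.3% (25.5 to 61.1)
- 1 negative: 10/26 = 38.5% (22.4 to 57.5)

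**Extreme case.** With no conversion at all and 4 Day 0 negatives who stay negative, the endpoint as written reports 4/26 = 15.4%. Among Day 0 positives it is 0/22.

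**What the planned tables can show.** SAP 7.9.5 tabulates culture by timepoint, including Day 0, against DNA result and against clinical cure, so the number culture-negative at Day 0 will be visible. It does not cross Day 0 culture with follow-up culture. With x women negative at follow-up and none missing, conversion among Day 0 positives is only bounded, between (x − k)/(26 − k) and x/(26 − k). For x = 13 and k = 4 that is 9/22 = 40.9% to 13/22 = 59.1%. Neither SAP 7.9.3 nor 7.9.5 specifies a Day 0 count for hyphae.

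**The case against.** The plan never says these endpoints measure conversion. Mycological cure is defined as no *Candida* at follow-up, endpoint 3 spells out a negative culture, and endpoint 9 claims only absence. On this view the concern substitutes its own estimand. That is fair as far as it goes: there is no contradiction in the text, and the FAS rates are valid for what they literally state. But in a single-arm study a rate called cure will be read as change, and the plan offers no estimate that separates the two.

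Planned output also covers part of the gap. The 7.9.5 tables bound the culture result, and the individual listings in SAP 7.1.1 would let a reader trace about 26 women one by one. This lowers the stakes, but a bound or a listing is not an estimate with an interval. The Data Display Plan holding the mock tables is not among the documents, so it cannot be relied on either way.

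The size is hypothetical. Nothing in the documents supports any particular k, every entrant must be microscopy-positive, and the sign can reverse. All of that stands. SAP 6.6 and Protocol 10.1.1 also treat presence of hyphae as the preliminary diagnosis, so the documents are not uniform on hyphae-free entry, although criterion 3 plainly allows it.

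Finally, SAP v2.0 was signed on 25 March 2024, after the planned last visit in Q3 2023 (synopsis) or Q4 2023 (Protocol 13.7), so true pre-specification may no longer be possible. Actual completion and lock dates are not given; the fix allows for this.

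**Conclusion.** The concern holds, at minor severity. Following the plan exactly, women negative on a test at both Day 0 and follow-up count as successes on endpoints 8 and 9, and on endpoint 3 if clinically cured. No specified analysis isolates conversion.

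The size is unknown. The calculated shifts for endpoints 8 and 9 run from −3.8 to +13.5 points, and all rest on assumed k, p and q with N = 26 and none missing. The endpoint 3 figures also assume that clinical cure is independent of culture. The intervals in the worked example overlap heavily. With no Day 0 negatives there is no effect. The primary endpoint, its test and the sample size are unaffected.

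**What to change.** In SAP 7.9.3, keep the FAS rates as the main analysis and add supportive rows with Wilson 95% intervals:
- endpoint 8 (Day 7-14 and Day 25) and endpoint 3, in FAS women culture-positive at Day 0
- endpoint 9, in FAS women with hyphae at Day 0

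Beside each FAS rate, state how many women were negative on that test at Day 0. Footnote the FAS rates of endpoints 3 and 8 as meaning culture-negative at follow-up, not conversion. Use one definition of hyphae at both visits, and say how pseudohyphae and the *traced* result in SAP 6.6 are counted; the endpoint 9 row cannot be built without this.

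List the addition in SAP 7.10. The FAS stays the main set and the endpoint definitions do not change, so under SAP 2 recording it in the SAP should suffice. If the database is already locked, present the rows as supplementary and document them in the CIR, as Protocol 12 provides for deviations from the planned analysis.

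The cost is four table rows, the Day 0 counts, two footnotes and a hyphae rule, all from data already scheduled. The downside is smaller denominators: at a 50% rate the Wilson interval is 35.9 points wide at n = 26, 37.8 at n = 23 and 39.3 at n = 21.

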7.9.4 Adverse events

Adverse events will be coded according to MedDRA.

An overview of all adverse events will be presented, including the number and percentage of subjects with at least one, and the total number, of the following:

- Adverse events.
- Serious adverse events.
- Adverse events leading to withdrawal of the investigational product.
- Fatal adverse events.
- Adverse events, broken down by severity.
- Adverse events, broken down by causality assessment.

The incidence of adverse events will be presented by system organ class and preferred term. For each system organ class and preferred term, the total number of adverse events as well as the number and percentage of subjects with at least one adverse event in that system organ class or preferred term will be presented.

7.9.5 Exploratory endpoints

The endpoint

- Correlation between bacterial vaginal microbiome as assessed by vaginal swab DNA-analysis on Days 0, 7, 14, and 25 and clinical cure.

will not be analysed by CTC. Hence, it is not elaborated on further in this SAP.

The endpoint

- Correlation of presence of fungus as analysed by vaginal swab DNA-analysis on Days 0, 7, 14 and 25 and presence of fungus as assessed by culture

will be addressed descriptively in a frequency table by timepoint. Results will be presented for each fungus species and overall, for any fungus in culture or swab DNA-analysis respectively.

In addition, to assess magnitude of shifts over time the value of fungus as analysed by vaginal swab DNA-analysis will be summarised per timepoint stratified by the magnitude of fungus as assessed in culture, with the latter being expressed as weak, moderate or abundant growth. Results will be presented for each fungus species. The endpoints

- Correlation of presence of fungus as analysed by vaginal swab DNA-analysis on Days 0, 7, 14 and 25 and clinical cure.
- Correlation of presence of fungus as assessed by culture on Days 0, 7, 14 and 25 and clinical cure.

will be addressed descriptively by frequency tables by timepoint. In addition, the magnitude (value) of fungus as analysed by vaginal swab DNA-analysis will be summarized descriptively per timepoint stratified by clinical cure. Furthermore, the relationship between magnitude (value) of each fungus species analysed in culture, and expressed as weak, moderate or abundant, and clinical cure will be summarised descriptively in a frequency table.

Statistical Analysis Plan

Study ID: CL4

Additionally, number of previous infections (0-1, 2 or 3) will be correlated to levels of fungus as analysed by vaginal swab DNA-analysis by summarizing the latter descriptively per timepoint stratified by previous infections.

Change in vaginal pH will be presented with descriptive statistics overall and separately for clinically cured and not clinically cured patients. A decrease from baseline in vaginal pH will indicate appropriate release duration.

All analyses described in this section involving clinical cure will be done for clinical cure as defined in the primary endpoint, i.e. over the period Day 7-14, as well as for clinical cure at Day 7 and 14 respectively.

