5.4.5 Day 14 (± 2 days); Follow-up visit

Patients with clinically and mycologically cured VVC at Day 7, or patients initiating rescue treatment Day 7 (even if they are clinically cured according to the CIP), will not perform the Day 14-visit. For these patients, this visit will be omitted.

Patients without clinically and mycologically cured VVC at Day 7 will visit the clinic on Day 14 to have gynaecological examination performed. The Investigator or an authorised designee will assess the presence of vulvovaginal signs (erythema, oedema, and excoriation) and symptoms (itching, burning, and irritation) and score each sign and symptom on a scale of 0 to 3 (see [Section 9.1.2](#)).

Vaginal samples will be examined under a microscope for yeast forms (hyphae or pseudohyphae) or budding yeast. Vaginal secretion samples collected by swabs will be used for culture and for sequencing analysis of the vaginal microbiome. If the patient is menstruating at this timepoint, the visit should be postponed until menstruation is over.

The Investigator or delegatee will ask the patient about potential menstruation onset.

Procedures to be performed:

- Gynaecological examination by Investigator or authorised designee, evaluating vulvovaginal signs (erythema, oedema, and excoriation) and symptoms (itching, burning, and irritation) according to the scoring scale (0 to 3).
- Fungal microscopy assessment (KOH or saline preparation)
- Vaginal swab for
 - Culture
 - Sequencing
- Recording of:
 - Concomitant medications
 - AEs
 - Potential menstruation onset

Rescue treatment, according to standard clinical practice, will be offered if the intensity of VVC symptom is the same or higher compared to the inclusion visit (Visit 1, Day 0). See details in [Section 7.5.2](#).

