5.1 Sample Size

Assuming a true proportion of 54% clinically cured in the treated group a sample size of 24 patients is needed to obtain 80% power to show that the one-sided 95% confidence interval (CI) for the clinical cure rate is above 30%. To compensate for patients with missing data a total of 26 patients will be included.

Statistical Analysis Plan

Study ID: CL4

6 Assessments

An overview of the assessments performed during the study are presented in Table 1.

Table 1. Schedule of assessments and procedures

Evaluations	Day 0	Day 0-5	Day 6	Day 7 (+2 days)	Day 11 (±1 day)	Day 14 a (±2 days)	Day 25 (±3 days)
	Screening	Treatment	Follow-up	Follow-up	Follow-up	Follow-up	Follow-up
	Visit 1		At home	Visit 2	At home	Visit 3	Visit 4 (Telephone)
Informed consent	X						
Demography	X						
Eligibility criteria	X						
Pregnancy test (urinary)	X						
Medical and surgical history	X						
Prior and concomitant medications	X			X		X	X
Menstruation (date of end/onset)	X			X		X	X
Gynaecological examination incl. CVVS	X			X		X	
Vulvovaginal symptoms (via patient questionnaire or telephone)		X	X		X		X
Fungal microscopy assessment	X			X		X	
Vaginal swab for culture ^b	X			X		X	X
Vaginal swab for sequencing ^b	X			X		X	X
Treatment dispensing	X						
Treatment with Gedea Pessary ^c		X (Daily)					
Vaginal pH (pH strip test)	X			X			
Patient questionnaire/Usability			X				
AEs				X		X	X
Product accountability ^d				X			
Rescue treatment				X ^e		X ^e	X ^f

^a Only for patients with no clinical and mycological cure Day 7.

^b Self-swab on Day 25(presence of Candida + sequencing analysis of the vaginal microbiome).

^c Treatment to be self-administered by the patient at home, at night before going to bed.

^d Patients should be asked to return all used and not used treatment packages.

^e Offered if the VVC symptom score on that day is equal to or higher than the score at the inclusion visit (Day 0).

^f If symptoms recur on Day 25, or symptoms persist, rescue medication could be offered according to standard clinical practice.

Statistical Analysis Plan

Study ID: CL4

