7.9.2 Primary Variable

The primary endpoint is the clinical cure rate on Day 7-14, which is defined as the percentage of patients clinically cured at Day 7 to Day 14.

Clinical cure is defined as the absence of signs and symptoms of VVC in terms of having a CVVS score ≤ 3 .

Each of the following 6 vulvovaginal signs and symptoms will be individually scored using the scoring scale below.

- Vulvovaginal signs: erythema, oedema and excoriation
- Vulvovaginal symptoms: itching, burning and irritation

Scoring scale: each score should be objectively defined:

- 0 = none (absent)
- 1 = mild (slight)
- 2 = moderate (definitely present)

Study ID: CL4

3 = severe (marked, intense)

The CVVS score is the sum of the 6 individual scores. If any of the 6 individual signs and symptoms are missing, then the CVVS score will be considered missing. The last non-missing assessment of CVVS in the interval of Day 7-14 will be used. However, if the patient received rescue medication between the CVVS assessments at Day 7 and 14, CVVS data from Day 7 will be used. The same derivation will be made for secondary and exploratory endpoints made during the same time interval Day 7-14.

In the estimand setting, the primary endpoint will take the following identified intercurrent events into account:

1. Concomitant anti-fungal therapy or other treatments related to VVC due to lack of clinical performance prior to CVVS evaluation used for the primary endpoint definition.
2. Treatment discontinuation due to lack of clinical performance.
3. Rescue medication prior to the CVVS evaluation used for the primary endpoint definition.

Rescue medication prior to the CVVS evaluation used for the primary endpoint definition. From a practical perspective, bullet points 1 and 3 above will be regarded as the same in this study. Applying the composite strategy to account for these intercurrent events, these have been incorporated in the endpoint definition. Thus, to be defined as clinically cured on Day 7-14, the patient needs to have the last available CVVS score equal to or below 3 at Day 7-14, and that none of the above stated intercurrent events have occurred. If the CVVS score is above 3, or any of the intercurrent events has occurred, the patient is defined as not clinically cured on Day 7-14.

Patients with missing CVVS score at Day 7-14 and no intercurrent events will be considered as missing in the analysis.

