The primary endpoint clinical cure rate on Day 7-14, as defined in the section will be calculated and presented together with a one-sided 95 % CI based on the Wilson score.

The primary performance objective of the trial is to show that the clinical cure rate is above 30 %, i.e. to show that the lower limit of the one-sided 95 % CI for the observed cure rate is above 30 %.

Hypotheses for the primary clinical performance endpoint

Null hypothesis: Clinical cure rate is less than or equal to 30 %.

Alternative hypothesis (one-sided): Clinical cure rate is above 30 %.

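### SAP 7.9.5: the two culture-grade tables have no place for women whose culture turns negative, and the Day 14 fungus-by-cure tables cover a group selected on both variables

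*SAP*

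**What the plan says.** **Culture grade.** SAP 7.9.5 introduces one table as a way to judge how far fungus levels move over time. At each timepoint it summarises the DNA value, "stratified by the magnitude of fungus as assessed in culture, with the latter being expressed as weak, moderate or abundant growth". A later table in the same section crosses the same three grades with clinical cure. SAP 6.6 describes what is recorded from culture as "Vaginal swab culture result (positive, negative) and species present" and mentions no growth grade.

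**Day 14.** Protocol 5.4.5 names those who skip the visit: "Patients with clinically and mycologically cured VVC at Day 7, or patients initiating rescue treatment Day 7". Protocol 5.4.3 likewise cancels it once both cures are established. SAP Table 1, footnote a, repeats the part of the rule that concerns cured women. SAP 7.9.5 nevertheless plans fungus-by-cure tables at Days 0, 7, 14 and 25, with cure defined over Day 7-14, at Day 7 and at Day 14.

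**Handling rules.** SAP 7.9.2 takes the last non-missing score in the interval and adds: "The same derivation will be made for secondary and exploratory endpoints made during the same time interval Day 7-14". SAP 7.1.5 plans, in general, no imputation.

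**The concern.** These are two separate problems with different causes.

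(a) A negative culture is this trial's definition of mycological cure, yet it has no row in either culture-grade table. The strata are also re-formed at each visit from whoever still shows growth. A woman who goes from abundant to weak changes stratum; a woman who clears leaves the table. What results is a series of cross-sections, although the stated purpose is to show change.

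(b) If attendance follows the protocol, every woman clinically cured at Day 7 who is sampled at Day 14 was culture-positive at Day 7, unless there is no Day 7 culture result. The cell that most supports a link between clearing *Candida* and being cured has been removed by design. Any table using cure at Day 14 inherits this, because the omitted women have no Day 14 score. The stake is the SAP's exploratory objective (3.3) of relating fungus to clinical cure: a reader could conclude from the Day 14 table that cured women carry more *Candida*, when the pattern comes from who was sampled.

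**Working it through.** The plan gives no figure on this point. Its only design figure is the sample size, and it reproduces: n = [(1.645√(0.30×0.70) + 0.842√(0.54×0.46))/0.24]² = 23.9, so 24, with 26 enrolled. Only the 26 is used below. All culture, DNA and persistence inputs are assumptions, since the documents give none.

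**(a) Missing level.** Assume mean DNA values of 0.5, 2, 4 and 6 for none, weak, moderate and abundant growth, with 2/4/8/12 women at Day 0 and 13/5/5/3 at Day 7.

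- Day 0, all women: (2×0.5 + 4×2 + 8×4 + 12×6)/26 = 113/26 = 4.35.
- Day 7, all women: (13×0.5 + 5×2 + 5×4 + 3×6)/26 = 54.5/26 = 2.10, a fall of 2.25.
- Displayed strata: means 2, 4 and 6 at both visits; women shown fall from 24 to 13.

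If 30-70% of 26 women are culture-negative at Day 7, about 8 to 18 women are absent from both tables.

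**(b) Selection, crossing Day 7 cure with Day 14 culture.** Assume 50% cured at Day 7; Day 7 culture negative in 70% of cured and 40% of uncured women; negatives stay negative 80%; positives turn negative 30%; no rescue.

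| Day 14 culture negative | Cured | Uncured |
|---|---|---|
| All women, if sampled | 0.7×0.8 + 0.3×0.3 = 65% | 0.4×0.8 + 0.6×0.3 = 50% |
| Attenders | 30% (all were positive at Day 7) | 50% |
| No Day 7 association (50% negative in both groups), all women | 0.5×0.8 + 0.5×0.3 = 55% | 55% |
| No Day 7 association, attenders | 30% | 55% |

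**(b) Same inputs, crossing Day 14 cure with Day 14 culture.** Add that 90% of Day 7-cured women stay cured, and that uncured women become cured at 60% if Day 7 culture-negative and 25% if positive. As shares of all women, the attending Day 7 cells are cured/positive 0.15, uncured/negative 0.20 and uncured/positive 0.30; the omitted cured/negative cell is 0.35.

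- Attenders, cured: (0.135×0.3 + 0.12×0.8 + 0.075×0.3)/0.33 = 0.159/0.33 = 48%.
- Attenders, uncured: (0.015×0.3 + 0.08×0.8 + 0.225×0.3)/0.32 = 0.136/0.32 = 43%.
- All women, cured: (0.159 + 0.315×0.8)/(0.33 + 0.315) = 0.411/0.645 = 64%.
- All women, uncured: (0.136 + 0.035×0.8)/(0.32 + 0.035) = 0.164/0.355 = 46%.

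The gap shrinks from about 17 points to about 6 but keeps its sign.

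**Range.** Take 26 women at Day 7 with cured/negative 10, cured/positive 4, uncured/negative 4 and uncured/positive 8. The odds ratio is 10×8/(4×4) = 5.0 and phi = 64/168 = +0.38. Attenders are 0/4/4/8, with phi = -16/48 = -0.33. Over cure rates of 41-54%, culture-negative rates of 30-70% and Day 7 odds ratios of 2-9, phi on Day 7 status runs from +0.15 to +0.50 in all women and from -0.18 to -0.51 in attenders. Now let a share of attenders keep their Day 7 status and redraw the rest from the full Day 7 distribution. The Day 14 odds ratio falls below 1 only when that share exceeds about 0.37-0.46 (Day 7 odds ratio 2), 0.62-0.71 (4) or 0.81-0.86 (9).

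**Does the last-available rule cure it?** Not fully. Take no association, 25% of women in each Day 7 cell and a share of 0.8 in the same model. Each attending cell ends at 0.8×0.25 + 0.2×0.75×0.25 = 0.2375. Cured/negative ends at 0.25 + 0.0375 = 0.2875, because those women are frozen at Day 7. The odds ratio is 0.2875/0.2375 = 1.2 where the truth is 1: a small bias in the opposite direction.

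**The case against.** The strongest reply is that little is lost. Only two of the fungus summaries in 7.9.5 use the growth grades. The presence tables (DNA against culture, DNA against cure, culture against cure), DNA value by cure and DNA value by previous infections all keep culture-negative women. SAP 7.9.3 reports mycological cure and combined clinical and mycological cure with Wilson intervals. A reader might infer that clearance goes unreported, or that the trial has no other link between culture and cure; neither is so. This part of the reply stands and limits point (a) to the two tables.

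Table shells sit in a Data Display Plan that is not among the documents and may already hold a no-growth row. That is possible, but the SAP text should say so. A reader might also infer that the growth grade was never collected. SAP 6.6 does not list it, but that shows only that its source is unstated.

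On (b), a reader might infer that the Day 14 table must show the wrong sign. The second calculation shows otherwise, and the values that decide it are not in the documents. The SAP also discloses part of the attendance rule in Table 1. Disclosure tells the reader who attended; it does not make the comparison interpretable. Nor does the last-available rule clearly replace the separate Day 14 tables, which 7.9.5 requests explicitly.

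Finally, these are descriptive analyses in about 26 women, with no test and no decision resting on them. That is correct and sets the weight of the point.

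**Conclusion.** Both points hold in limited form.

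(a) As worded, the two culture-grade tables drop women whose culture turns negative, and the table meant to show shifts computes none. This follows from the text alone; the number of women affected does not, and 8 to 18 of 26 rests on an assumed 30-70% negative at Day 7.

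(b) The Day 14 fungus-by-cure tables, and any table using cure at Day 14, are selected on both variables. The omission of cured-and-negative women pulls the association towards cured women carrying more *Candida*. Reversal is possible and not certain: it depends on the strength of the Day 7 association and on how stable status is from Day 7 to Day 14. The illustrations set rescue to zero; the further omission of women starting rescue at Day 7 is a second selection whose size and direction the documents do not fix.

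The two points are independent: a no-growth level would not repair Day 14, and relabelling Day 14 would not repair the shift table. The primary endpoint is untouched.

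**What to change.** In SAP 7.9.5 and the table shells:

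1. Add a no-growth level to both culture-grade tables.
2. Add a paired table of culture grade at Day 0 against grade at each later visit, per species, with the paired change in DNA value.
3. State where the growth grade comes from (eCRF field or laboratory transfer), and align SAP 6.6 with it.
4. Make the Day 7 culture-by-cure and DNA-by-cure tables the main version, since all women are scheduled to attend then.
5. Give the last-available Day 7-14 tables as supportive, with a note that women cured on both counts at Day 7 are not re-assessed.
6. Keep the Day 14 tables, which are named in the endpoints. Label them, and any table using cure at Day 14, as covering only women not cured on both counts at Day 7 and not started on rescue then, with no association to be inferred.

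The cost is a few extra shells, one variable to trace, and a less prominent Day 14 table. No visit or sampling procedure changes.
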